Effects of a Numerical Superiority and Inferiority Tactical Training Program Compared to
Conventional Training on Procedural Tactical Knowledge and Executive Functions in
Soccer Players. A Randomized Controlled Trial

Date: September 9th, 2023

Protocol

There is a great need to establish reliable evaluation and intervention protocols to improve the tactical component, decision making (TD) and procedural tactical knowledge (PTK) in Soccer.

Objectives

To determine the effects of a tactical training program of numerical superiority and inferiority during 12 weeks of follow-up on the PTK, which will be evaluated by calculating offensive, defensive and global effectiveness indices (EI) of 24 male amateur soccer players, as well as the effect on their executive functions.

Type of study

The study corresponds to a predominantly quantitative approach. According to Friedman et al., (2010) it is a prospective, experimental study, in parallel, with 2 randomized groups (experimental and control). The study is a repeated measures design because measurements of the most important outcomes (primary and secondary) will be performed at four times: pretest (week 1), intermediate test 1 (week 6), intermediate test 2 (week 11) and posttest (week 16).

Site Selection (Context and Access)

The study is being carried out with soccer players from a club that competes in the Antioquia Soccer League who train on fields in the city of Medellín, which are made of synthetic grass and natural grass. These fields are in good condition and offer adequate technical conditions and security for soccer players.

Population

The investigation is being carried out with amateur soccer players, male, in the First B departmental category.

Selection criteria

Inclusion criteria

Soccer players belonging to a soccer club.

Soccer players playing roles of outfield (all except goalkeepers).

They compete in the First B category of the Antioquia Football League in the 2023 season.

Players aged between 17 and 26 years.

Players with at least six months of experience in federated soccer.

Players who do not present cognitive disorders that make learning difficult, which can be identified through monitoring by the coaches and/or tests carried out by the Neuropsychology staff.

They must be affiliated to the health system of the contributory or subsidized regime.

They must agree to participate in the study after knowing and signing the consent or informed assent as appropriate.

Exclusion criteria

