The guidelines of the Declaration of Helsinki (updated at the 64th general assembly in Fortaleza in 2013) and of the Ministry of Health and Social Protection of Colombia through resolution 8430 of 1993 will be followed. All measures will be provided to guarantee the confidentiality of the data of the participants by assigning codes. All participants and their legal representatives (for minors) were informed of the particularities of the research through informed consent and/or assent regarding exposures, expected results, and contributions to the academic and sports field. The results obtained will be returned to the participants, their relatives and/or legal representatives and the participating soccer club. The endorsement of the research bioethics committee of the Institute of Physical Education and Sport (IUEFD) was obtained (ACEI 39-2023, June 20th, 2023). The present investigation is classified in the category of minimum risk according to article 11 of resolution 8430 of 1993 of the Ministry of Health of Colombia. In any case, the development of this research does not represent an additional risk to the activities, training sessions and competitions in which the soccer players participate daily.

Interventions (GE and GC Training Plans)

GE (Tactical Training in Numerical Superiority and Inferiority)

The participants of the GE will carry out a specific training program, with the objective of improving both offensive and defensive technical and tactical action (ATT) that allow the increase of the IE (offensive and defensive). The formats through which the GE subjects will train are Small Sided Games (SSGs) and ATT 2v1, 3v2 and 4v3, alternating them during the week (SSGs on Tuesdays and ATT on Thursdays). It is important to mention that, in terms of physical demand, the training through these 2v1 and 3v2 formats are similar, and therefore, can be assimilated in part, to those proposed by Casamichana and Castellano (2016) to the SSGs of level 14 and level 16 (on a scale from 1 to 20, with 20 being those with the greatest physical demand), in which the JER of 1v1 and 2v2 present the following specifications: Level 14: 2 series X 6 repetitions X 1'30" of

exercise X 1' 30" pause (total 12 repetitions of SSGs) and Level 16: 2 series X 7 repetitions X 1'30" of exercise X 1'30" of rest (total 14 repetitions of SSGs).

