In the event that one of the subgroups is missing player(s) to perform the repetitions set out in the protocol, due to any circumstance (non-attendance to the session, physical discomfort, momentary bruises, injury or unexpected situations), their replacement will be arranged with other soccer players who are not part of any of the comparison groups (GE and GC), they can be students of the IUEFD of the University of Antioquia (UdeA) with experience as soccer players and who previously know the ATT to be developed and also soccer players who are on trial within the team. For the registration, quantification and monitoring of the number of repetitions, a coach will be arranged so that each time the soccer players in each of their subgroups execute a repetition, he will write it down on forms designed for that purpose. Once the participants have completed the number of repetitions stated in the protocol, this coach will finish this part of the training.

After the specific stimuli oriented to actions and situations of numerical superiority and inferiority, the coaches will possibly perform other training stimuli not considered in the study; however, they will be asked not to perform additional JER or ATT training in numerical superiority and inferiority, nor ATT 1v1, 2v2, or 3v3 during the duration of the experiment to avoid co-interventions that could generate bias. It is important to mention that the coach who will execute the EG training program will be different from the one who will execute the CG training program to avoid intervention bias.

GC (Conventional Training of ATT in numerical equality)

The CG participants will perform conventional training. In the present study, ATTs that are performed in numerical equality in 1v1, 2v2 and 3v3 formats are called conventional training. Similarly, coaches will be asked not to carry out additional specific training with these formats, nor offensive or defensive SSGs or ATT in numerical superiority or inferiority, specifically in 2v1, 3v2, or 4v3 formats, during the duration of the study, to avoid confounding biases due to possible co-interventions. This GC training program will include individual, pair and trio ATTs.

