Regarding the training plans (intervention protocols) to be compared, pilot tests of the training sessions were implemented in the same way as established in the protocols and with the same people responsible of each activity. The coaches will carry out the exercises and sessions of the GE and GC following the parameters of the stimuli, repetitions, volume, order, sequence, behavior, registration, and verification of compliance established in the protocol.

Participants will carry out the exercises and sessions as indicated by the coaches. Three weeks of training were carried out simulating the conditions described in the protocols (GE and GC). In week 1, the 2v1 JER and ATT formats were taking place, in week 2 the 3v2 SSGs and ATT formats were developed, and in week 3 the 4v3 SSGs and

ATT formats were taking place. These pilot tests were carried out with the same group under investigation during the last month prior to the start of the research.

Similarly, pilot tests of the FOCOS evaluation protocol were carried out. In this sense, the tests were carried out under the same conditions as set out in the protocol described above, on the same field, at the same time and with the people in charge of carrying out each of the activities (coaches, filming the test and assistants), in the same way, these pilot tests were carried out with the same participants with which the research will be carried out to familiarize the soccer players. Regarding the equipment, the procedures were also standardized with the same drone to be used and with the same person who will handle the drone during the investigation and, in addition, with the same implementation and clothing such as balls, demarcation cones and training bibs.

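### The three-week pilot trained the trial's own players in every experimental format before the pretest, so the conclusion should be limited to 12 further weeks in pre-exposed players and rest on the between-arm contrast

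*Combined protocol and SAP*

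**What the plan says.** The Objectives section frames the trial as follows: "To determine the effects of a tactical training program of numerical superiority and inferiority during 12 weeks of follow-up on the PTK". Tests fall in weeks 1, 6, 11 and 16, and week 1 is the pretest.

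Pilot Testing Procedures describes what happened before week 1. On fidelity it says that "pilot tests of the training sessions were implemented in the same way as established in the protocols". On length it says: "Three weeks of training were carried out simulating the conditions described in the protocols (GE and GC"). The week-by-week list opens with "In week 1, the 2v1 JER and ATT formats were taking place, in week 2 the 3v2 SSGs and ATT formats were developed". The third and last week was given to 4v3, again both as small-sided games and as technical-tactical actions (ATT). On who and when: "These pilot tests were carried out with the same group under investigation during the last month prior to the start of the research".

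The Interventions section gives the GE formats as "Small Sided Games (SSGs) and ATT 2v1, 3v2 and 4v3, alternating them during the week". For the control group, "ATTs that are performed in numerical equality in 1v1, 2v2 and 3v3 formats are called conventional training". Coaches are asked to keep 2v1, 3v2 and 4v3 work away from GC players while the study runs, because such co-intervention could confound the comparison.

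The plan does not say whether allocation came before or after the pilot, which players did which format, or how long the gap to the pretest was. Pilot exposure is not among the confounders listed under Confounding Bias Control, and Analysis of data has no step for it.

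**The concern.** The pilot list contains every GE format and no GC format, although the pilot is said to simulate both arms. The trial players therefore had the experimental stimulus, at trial fidelity, shortly before the measurement from which change will be judged. Three weeks of training inside a month of about 30 days leave at most 30/7 - 3 = 1.3 weeks before the start.

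This matters most for the analyses that look at change within an arm. For executive functions, Analysis of data plans a paired pretest-posttest test in each group. For the effectiveness indices (IE) it plans repeated-measures ANOVA or Friedman over the four times and names no group term; Friedman has no between-arm comparison. Any gain made during the pilot is already in the pretest, so these analyses do not measure the programme from its start.

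The between-arm comparison is affected differently according to when and to whom the pilot was given, and the documents leave that open.

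**Working it through.** **1. Programme and calendar.**
- Tests in weeks 1, 6, 11 and 16 leave weeks 2-5, 7-10 and 12-15, which is 12 training weeks.
- Two sessions a week give 12 × 2 = 24 sessions.
- GC volume: 24 × 40 min = 960 min, as stated.
- GE volume: 24 × 30 to 42 min = 720 to 1,008 min, which contains the stated 920.

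**2. Size of the pilot, if run at protocol dose.**
- 3 × 2 = 6 sessions; 6/24 = 25% of the planned number.
- 6 × 30 = 180 min to 6 × 42 = 252 min; 180/920 = 20% and 252/920 = 27%.

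**3. Pilot common to both arms, or before allocation.** Exposure is then shared, or balanced in expectation by the 1:1 randomisation. The GE-GC contrast estimates the effect of 12 more weeks of GE against conventional training in players with recent exposure. If gains are linear and additive, the shared pilot cancels. If learning saturates or carries over unevenly, the contrast may shrink. The documents give no figure for this, so only a sensitivity range is possible.

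The plan's sample size reproduces first: difference 1.13, SD 0.81, d = 1.13/0.81 = 1.395. Two-sided alpha 0.05 is taken from Analysis of data, since the sample-size section gives none. The noncentral-t calculation gives 12 per arm for 90% power (actual 90.4%). With the difference reduced by an assumed fraction, at 12 per arm:

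| Assumed dilution | Difference | Power |
|---|---|---|
| 0% | 1.130 | 90.4% |
| 10% | 1.017 | 83.6% |
| 20% | 0.904 | 74.3% |
| 30% | 0.791 | 62.8% |

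**4. Pilot by arm, after allocation.** Week 1 then follows 3 weeks of differential training, and week 16 follows 3 + 12 = 15. Let E(t) be the GE-GC effect after t weeks of exposure, with no loss over the gap. The target is E(12). Change from week 1 gives E(15) - E(3).
- Linear, E(t) = bt: 15b - 3b = 12b = E(12). Loss 0%.
- Exponential, E(t) = A(1 - exp(-t/τ)): E(15) - E(3) = A·exp(-3/τ)·(1 - exp(-12/τ)) = exp(-3/τ)·E(12). Loss = 1 - exp(-3/τ).
  - τ = 6 weeks: 1 - exp(-0.5) = 39%.
  - τ = 4 weeks: 1 - exp(-0.75) = 53%.

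The time constants are assumptions; nothing in the documents fixes them. In this case the week-16 contrast itself is E(15), not E(12). It is larger by 15/12 - 1 = 25% if gain is linear, by (1 - exp(-2.5))/(1 - exp(-2)) - 1 = 6% for τ = 6, and by (1 - exp(-3.75))/(1 - exp(-3)) - 1 = 3% for τ = 4.

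**The case against.** The best defence is randomisation. If the pilot preceded allocation, or was identical for everyone, it cannot bias the GE-GC contrast; it only narrows the players to whom the result applies. Familiarising participants was the stated purpose of the pilot. Entrants already have at least six months of federated soccer, and the plan nowhere calls week 1 an untrained baseline. The restriction on GC formats applies while the study runs, so a pilot before the study broke no rule. Equal prior exposure dilutes the contrast only if learning saturates or carries over unevenly.

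All of this stands for the between-arm contrast when the pilot was common or came first. It does not help the within-arm analyses, and it does not cover a pilot given by allocated arm. The text does not settle which happened. The reference to the whole group under investigation suits a common pilot; the mention of both GE and GC conditions, with the same staff responsible for each activity, suits a pilot by arm.

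A reader might infer that the trial cannot measure the effect of a 12-week programme at all. The documents do not support that: a randomised comparison of 12 further weeks remains estimable when the pilot was common or preceded allocation. A reader might also take the pilot's share of 15 weeks, 3/15 = 20%, as the part of the effect that is lost. That uses a 15-week total, whereas the objective is a 12-week effect, for which the linear loss is zero.

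**Conclusion.** The point holds in limited form. It is explicit in the text that the trial's own players were trained in all GE formats within the month before the start, and that no washout, adjustment or order relative to allocation is given. Week 1 is therefore not an unexposed baseline, and within-arm change from week 1 does not measure the programme from its start.

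The consequence for the arm comparison is conditional. With a common or pre-allocation pilot, the contrast is valid for 12 further weeks in recently exposed players, possibly diluted by an amount the documents do not give. With a pilot by arm after allocation, week 1 is post-treatment and GE has about 15 weeks of exposure. Change from week 1 then loses between nothing (linear gain) and about 39% to 53% of a 12-week effect (exponential gain, assumed time constant 6 to 4 weeks). The dose comparison assumes that the pilot ran at two sessions a week and protocol duration.

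**What to change.** 1. Restate the objective and the conclusion as the effect of 12 further weeks of GE training against conventional training, in players exposed to all GE formats in the preceding month.
2. Base the conclusion on the randomised between-arm comparison, for the effectiveness indices and for executive functions. Name the group comparison explicitly in Analysis of data, and report within-arm change from week 1 as descriptive only.
3. State whether the pilot came before or after allocation, and tabulate pilot sessions by arm and format. If it was given by arm after allocation, do not use week 1 as the baseline for change or as an adjustment covariate. Compare the arms at weeks 6, 11 and 16 (executive functions at week 16 only, since they are not tested in between), and describe week 16 as reflecting about 15 weeks of exposure.

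The cost is some rewording, one table, and a narrower claim. In the by-arm case the analysis also loses the precision that a week-1 baseline would have given, which matters with 12 players per arm.

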and in defense: tackle, interception, deterrence and relocation. In the same way, the operational principles are evaluated, in attack: maintaining possession of the ball, progressing towards the rival goal and scoring a goal, and in defense: recovering possession of the ball, avoiding the progression of the opponent and protecting the goal. Similarly, the specific principles are evaluated, in attack: penetration, offensive coverage, mobility in depth, width and length, and in defense: retardation, defensive coverage, balance, concentration and defensive unity. In addition, the result of the action can be established, both in defense and in attack, it is determined if the action in general was successful or wrong. If there are doubts in the valuation for any reason, it is qualified as improbable or that there are doubts.

FOCOS is a field test that allows evaluating soccer players in their natural and contextual environment through specific soccer situations, which guarantees its ecological validity. 2 goalkeeper teams (P) + 4 v 4 + P are formed. There are 2 games of 4 minutes X 1 minute pause between each game. The authors of FOCOS propose 2 formats with different playing areas depending on the age of the players. For children under 12 years old (25mt X 30mt and 6mt X 2mt goals) and for people over 12 years old (33mt X 40mt and 7.32mt X 2.44mt goals). In this research the format for over 12 years will be used.

It is important to indicate that the test is controlled and monitored by an expert coach, who has academic training at the doctoral level in the area of sports training, with practical experience as a former soccer player at a professional level, with more than 20 years of experience as a soccer coach and Licensed as a CONMEBOL PRO soccer coach, also trained in the FOCOS evaluation protocol, carried out by means of previous readings of the protocol, conversations with the author of the test, and carrying out three pilot tests, which allowed to refine, standardize, and modify the test looking for better performance of the soccer players.

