To obtain the data, the games must be filmed with a camera and later, carry out the respective analyzes and evaluations. In the present investigation, a DJI Fly drone is used, which is positioned 20m high just behind one of the goals, this location guarantees complete visibility of the ATTs executed by the participants and full coverage of the pitch. Once all the corresponding games have been filmed, the videos are downloaded, which are

sent to the video analyst who will carry out the respective analysis and data report in the database created for this purpose. For the analysis, the video analyst will use the LINCE PLUS video analysis software (Soto et al., 2019), which is available and freely accessible.

The FOCOS units of measure are:

Volume, which corresponds to the number of times the soccer player develops tactical behaviors in each category.

The IE is determined through the following formula:

$$IE = \text{Volume of successful tactical behaviors} / \text{Number of tactical behaviors developed in each category of analysis}$$

$$\text{Offensive IE} = \text{Sum of the IE of offensive tactical behaviors} / \text{Number of categories in which the soccer player developed offensive tactical behaviors}$$

$$\text{Defensive IE} = \text{Sum of the IE of defensive tactical behaviors} / \text{Number of categories in which the soccer player developed defensive tactical behaviors}$$

$$\text{Global IE} = \text{Offensive IE} + \text{Defensive IE} / 2$$

The global IE represents the PTK of each soccer player.

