Once the pilot test has been carried out and the videos of the SSGs of the FOCOS test have been obtained, the principal researcher will deliver them to the ATT and PTK evaluator (video analyst), so that through the LINCE PLUS video analysis software he can carry out the respective evaluations and record the data in the respective information bases. In this phase of the investigation, the evaluator must be fully familiar and trained in the management of the software and the ATT of the participants to determine their general tactical behavior. To achieve reliability in this process, the evaluator (video analyst) will be calculated the intra-observation stability index, which will be carried out through the test-retest reliability, for which Cohen's Kappa (k) of the data will be applied with a difference of five weeks in the evaluation of both records. When the evaluator obtains an agreement considered good (0.61 - 0.80) or very good (0.81 – 1.00) the videos will be evaluated and record the respective data.

Data Collection Procedures (Assessment Protocols)

To evaluate the PTK (offensive IE, defensive IE and global IE) the FOCOS test will was applied and it was carried out through the following protocol: the groups of soccer players were formed randomly. To randomize the participants and form the groups, the random assignment software <https://www.sealedenvelope.com/simple-randomiser/v1/lists> was used. In the same way, the teams that face each other were randomized so that it is chance that defines the formation of the groups and the confrontation of these.

The soccer players were undergoing conditioning to start the test, which consists of joint mobility and flexibility exercises for 10 minutes, basic technique exercises (passing, controls, driving, dribbling and shots) for 7 minutes and short sprint, struggles and disputes for the ball for 3 minutes. In total, this set-up phase lasts 20 minutes. Then they were assigned two minutes to finish getting ready, organizing, and getting ready for the execution of the test.

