research protocol, that is, pretest (week 1), intermediate test 1 (week 6), test intermediate 2 (week 11) and posttest (week 16). Likewise, the groups formed randomly and the confrontation between them determined by chance at all test will be respected. If for any reason a participant cannot take the test due to any circumstance (absence at the session, physical discomfort, momentary bruises, injury or unexpected situations), his replacement will be arranged with IUEFD student with experience as soccer players and who previously know the protocol to complete the gap, or with soccer players who are on trial at the club and who are not part of the comparison groups. The tests will be carried out on Wednesday from 6 to 8 in the morning in the respective weeks (1, 6, 11 and 16).

Once the tests have been completed and duly filmed, the respective videos will be passed on to the evaluator (video analyst) who will download the videos, analyze the different actions and behaviors developed by each of the participants through the LINCE PLUS video analysis software and record the data in Excel files in the database created for this purpose. This database will be created in such a way that a code is generated for the participants and no one can identify who the information registered and consigned there corresponds to (except the main researcher) who will save it on their personal computer, on a hard drive to keep copy and in the cloud. These files will be kept with a password, which only the principal researcher will know.

The information and data resulting from the respective analyzes carried out by the evaluator will be sent to the statistician who will proceed to carry out the respective analysis and application of tests in accordance with the data treatment that appears in the data analysis section.

Prior to carrying out the FOCOS test that evaluates the primary and secondary outcomes and, prior to the execution of the tests that evaluate executive functions (exploratory outcome), the following question will be asked to the participants: from 0 to 100, ¿How mentally fatigued are you? Being 0 (not at all fatigued) and 100 (maximum fatigue).

The evaluations of week 1 were carried out on two different days and in the following order: the first day the survey was carried out, mass, height, mental fatigue and finally, the tests were applied to assess the executive functions, for which participants were

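### FOCOS scores players against each other in chance-drawn teams with no stated balance by arm, so within-arm change in IE is not interpretable and the size of the GE-GC difference varies with the draw

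*Combined protocol and SAP*

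**What the plan says.** The section on PTK (Offensive IE, Defensive IE, Global IE) gives the test format: "2 goalkeeper teams (P) + 4 v 4 + P are formed". For each action, in attack and in defence, "it is determined if the action in general was successful or wrong". IE is the successful share of a player's own actions per category, averaged over the categories he used, and "The global IE represents the PTK of each soccer player".

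Under Data Collection Procedures, "the groups of soccer players were formed randomly", and opponents were also randomised, "so that it is chance that defines the formation of the groups and the confrontation of these". For the tests at weeks 1, 6, 11 and 16 the same section says that "the groups formed randomly and the confrontation between them determined by chance at all test will be respected". Gaps left by absent players are filled by students or by players "who are on trial at the club and who are not part of the comparison groups".

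The section does not say whether the draw runs across or within arms, or whether it is balanced by arm. It also leaves open whether one draw is kept or a new one is made each time. Team, opponent and match are absent from the list under Confounding Bias Control. Analysis of data plans a repeated-measures ANOVA or a Friedman test for the three indices, plus a MANOVA. That paragraph names no between-arm term for IE.

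**The concern.** The trial treats IE as a property of the individual player, but it is measured in direct opposition to other trial players. If GE training works, those who meet GE players have a harder test than they had at baseline, whichever arm they belong to. Two things are at stake.

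- **Within-arm curves.** A GC curve could fall, and a GE curve could rise too little, with no such change in the players themselves. The Friedman test compares time points and has no between-arm term, so on that branch the IE result would rest entirely on such curves.
- **Size of the arm difference.** If chance puts mainly GE players against mainly GC players, the difference is enlarged. If like meets like, it is reduced. Keeping one draw for all tests would never average this out.

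**Working it through.** **Inputs from the documents.** 24 players, 12 per arm; teams of four outfield players; mean difference 1.13 and SD 0.81; two-sided alpha 0.05. If everyone attends, this makes 6 teams and 3 matches (derived, not stated).

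**The plan's own figure.** Standardised difference 1.13/0.81 = 1.395. With 12 per arm the noncentrality is 1.395 × √(12/2) = 3.42 on 22 degrees of freedom, and the power is 0.904. This reproduces the chosen 24 players at 90%. The calculation treats the 24 scores as independent.

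**Assumed model.** A GE player truly gains d and a GC player does not change. Each player then loses λ × d × (share of GE players in the opposing team). The documents give no value for λ, so 0.25, 0.5 and 1 are shown; 1 is a full opponent effect. No stand-ins are assumed.

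**Average over free draws.** A player's opponents come from the other 23 players:

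- GE player: 11/23 = 47.8% GE opponents, so the apparent change is d(1 − 11λ/23).
- GC player: 12/23 = 52.2% GE opponents, so the apparent change is −12λd/23.
- Difference: d(1 + λ/23).

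**Spread over single draws.** In 40,000 simulated draws, the GE-opponent share of GE players minus that of GC players had mean −0.043 and SD 0.138. The central 95% ran from −0.33 to +0.25. The multiplier on the true arm difference is 1 − λ × (that quantity).

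| λ (assumed) | GE appears | GC appears | Mean GE-GC | Multiplier, central 95% of draws |
|---|---|---|---|---|
| 0.25 | +0.88d | −0.13d | 1.01d | 0.94-1.08 |
| 0.5 | +0.76d | −0.26d | 1.02d | 0.88-1.17 |
| 1 | +0.52d | −0.52d | 1.04d | 0.75-1.33 |

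At λ = 1 the multiplier is off by at least 1/6 in about 31% of draws. At the lower end, 0.75 of the planned effect, power with 12 per arm falls from 90% to 69%.

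**Kept or redrawn.** Averaging over four independent draws halves the SD, from 0.138 to 0.070. At any single test the spread is unchanged, and the within-arm shift remains either way.

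**Balanced teams.** With 2 GE and 2 GC in every team, all players face 50% GE opponents and the opponent term drops out of GE-GC exactly. A free draw gives one particular team this composition with probability C(12,2)²/C(24,4) = 4356/10626 = 0.41, and all six teams with probability about 0.017.

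**Type I error.** With no true difference the multiplier has nothing to act on. In simulation with assumed team ICCs of 0.1 to 0.3 (opposing teams mirrored) and a match ICC of 0.05, a t test on freely drawn teams rejected in 5.0% to 5.2% of trials.

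**The case against.** Three stronger readings are tempting, and the documents do not support them.

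- **The draw ignored arm.** A reader might infer this, but the text says only that chance set teams and match-ups. A restriction by arm is neither stated nor excluded. The silence does not rescue the plan: GE-only teams against GC-only teams would multiply the difference by 1 + λ (1.25 to 2.0), and the same simulation then gave a type I error of 13% to 27%.
- **One arm's gain is the other arm's loss.** IE is a ratio of a player's own actions and includes positioning and play away from the ball, so it is not strictly zero-sum. Under a free draw the opponents' loss also falls almost equally on both arms. A systematic transfer would need teams made up of one arm only.
- **The arm comparison is biased or prone to false positives.** On average it is off by only 1% to 4%, and under a free draw the rejection rate stays near 5%. Even at λ = 1 the multiplier is exactly 1 in 31% of draws and within 8.3% in 69%. Zero distortion does not require 2+2 teams, so their rarity should not be read as the rarity of a fair draw.

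A further objection concerns the remedy. The plan promises the same conditions at all four tests. If teams are kept, each player's change is measured with the same team-mates and opponents, and their baseline strength largely cancels. That advantage is real. Balanced teams largely answer it, because team and opponent strength cancel in the arm contrast at each redrawn test, but the pretest draw stays unbalanced.

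What stands is that scores are interdependent, team composition by arm and redrawing are unspecified, and the IE analysis has an option with no between-arm comparison.

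**Conclusion.** The point holds in a limited form. Within-arm change in IE cannot be read as improvement or decline of that arm, because it mixes the players' own change with that of their opponents. This applies to any draw in which the arms meet, and it matters most on the Friedman branch. The GE-GC contrast remains a sound basis for the conclusion if the draw is free of arm, but its size carries a chance multiplier. In a single kept draw this ranges from 0.94-1.08 (λ = 0.25) to 0.75-1.33 (λ = 1).

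These figures rest on an additive model, full attendance, a draw unrestricted by arm and assumed values of λ; the widest range is the upper case. The matter deserves correction before the remaining tests but does not invalidate the trial.

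**What to change.** 1. **Analysis.** State that the IE conclusion rests only on the between-arm (group-by-time) GE-GC contrast, and that neither the Friedman test nor within-arm change will be read as progress or decline. If normality fails, a between-arm test of change from pretest serves; the plan already names the Mann-Whitney test for executive functions. Cost: one or two sentences.
2. **Team draw.** At weeks 6, 11 and 16, draw teams at random with 2 GE and 2 GC players each. The independent person who holds the allocation should do this, so that the video analyst stays masked. State whether teams are redrawn at each test.
3. **Data.** Record team and opponents, including stand-ins, for each player at each test. Cost: two columns.

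The balanced draw has two drawbacks. Team-mates and opponents will differ from the pretest, whose draw adds some noise to change scores. In addition, 2+2 teams cancel opponent effects and effects shared by a whole team, but not a benefit passed between team-mates. A GE player has 1 GE player among 3 team-mates and a GC player has 2 among 3, so a spillover of γ × d × (share of GE team-mates) would multiply the contrast by 1 − γ/3. That is 0.92 at an assumed γ of 0.25. The factor is fixed and does not vary with the draw, and it should be acknowledged.

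If the sponsor prefers to keep the pretest teams, it should report each arm's realised share of GE opponents beside the result.
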